# **Statement of Compliance**

The study will be carried out in accordance with Good Clinical Practice (GCP) as required by the following:

- U.S. Code of Federal Regulations applicable to clinical studies (45 CFR 46)
- ICH GCP E6
- Completion of Human Subjects Protection Training

#### List of Abbreviations

AE Adverse Event

CFCS Communication Functional Classification System

CFR Code of Federal Regulations

CHAMP Children with Hemiparesis Arm and Movement Project

CIMT Constraint Induced Movement Therapy

CRF Case Report Form

CSA Combined Statistical Area

DSMB Data and Safety Monitoring Board FDA Food and Drug Administration

FWA Federal-Wide Assurance
GCP Good Clinical Practice
HEP Home Exercise Program
ICF Informed Consent Form

ICH International Conference on Harmonization

IRB Institutional Review Board

JTHFT Jebsen Taylor Hand Function Test

MOVE-IT Motivating Occupational Virtual Experiences In Therapy

MSA Metropolitan Statistical Area

N Number (typically refers to subjects)
OHRP Office for Human Research Protections

PI Principal Investigator

QUEST Quality of Upper Extremity Skills Test

RCT Randomized Controlled Trial

SAE Serious Adverse Event SUS System Usability Scale

TAM Technology acceptance model

UCT Usual Care Treatment

# **DRAFT**

# List of Abbreviations - continued

UE upper extremity
UVA University of Virginia
WMFT Wolf Motor Function Test

# **Protocol Summary**

Title: Motivating Occupational Virtual Experiences In Therapy (MOVE-IT) Phase II

Sites: University of Virginia (Charlottesville, VA) and Duke University (Durham, NC)

**Sponsor:** Barron Associates, Inc. (Charlottesville, VA)

**Study Design:** Rater-blinded randomized controlled study

**Population**: N: 48 Dyads\* (24 at each of 2 sites)

\*Dyad=One parent/legal guardian and one minor

Ages: 4 - 14 years (inclusive)

Sex: Any Race: Any

Diagnosis: Hemiplegia resulting from cerebral palsy, stroke, or other form of brain injury

Recruitment area: Charlottesville Metropolitan Statistical Area (MSA), Raleigh-Durham-Chapel Hill Combined Statistical Area (CSA),

and surrounding areas.

**Subject Duration**: 10-week intervention with 3 months follow up assessment.

Study Duration: Approximately 1 year

#### **Objectives**:

The primary Phase II investigational objective is to show a differential effect on the pre-to-post-intervention change in upper extremity (UE) motor function between an interventional group receiving the MOVE-IT home exercise program (HEP) and a usual care treatment (UCT) group, as assessed by the Jebsen Taylor Hand Function Test (JTHFT) and other gold-standard clinical assessments of UE function.

Blinded assessors, certified for the study instruments, will evaluate children in both groups at pre-treatment (baseline), immediate post-treatment (baseline + 10 weeks), and 3 months post-treatment. Assessments (3 total) will take place in an outpatient setting and include the following blinded instruments:

- Jebsen Taylor Hand Function Test (JTHFT) (primary outcome measure)
- Quality of Upper Extremity Skills Test (QUEST) (dissociated movements and grasp components)
- Wolf Motor Function Test (WMFT)

Additionally, parents will be asked to complete the following parental report instrument during each assessment visit:

• Pediatric Motor Activity Log (inventory of child's functional use of the UE)

For both groups, parents will be asked to maintain a weekly activity log, including activities

#### 2 BACKGROUND INFORMATION AND SCIENTIFIC RATIONALE

#### 2.1 Background Information

Virtual worlds-based games present a unique, innovative, and timely solution for supporting high-dosage evidence-based rehabilitation that targets neuroplasticity. There exists a substantial body of work on adaptations of VR for adult rehabilitation, much of which has focused on stroke [31], [32], [33], [34]. Studies involving children have not kept pace with adult applications and pediatric applications of VR have been relegated primarily to the academic realm. Preliminary results have shown some promise, both in terms of patient engagement and efficacy, but prior research lacks well-powered RCTs and has not been translated to clinical practice [35], [36], [37], [38], [39], [40], [41].

Barron Associates, Inc. (the NIH grantee for the MOVE-IT program) previously developed the Virtual Occupational Therapy Application (VOTA), an FDA-cleared software system that enables adult stroke patients to re-learn adult activities of daily living (ADLs), such as shopping or meal preparation, by practicing the physical movements within a virtual environment that reconstructs real-world tasks [42], [43] with Kinect-based human motion capture. VOTA has been shown to improve UE function in adult stroke patients [44], [45] and is now sold commercially as SaeboVR [46].

The MOVE-IT system, developed by Barron Associates, Inc. under NIH sponsorship, employs therapy games that combine virtual- and real-world physical elements to provide a solution suitable for both home use. MOVE-IT engages patients in repetitive practice, facilitating an evidence-based approach that integrates proven concepts in CIMT. MOVE-IT system consists of a multi-sensory smart toy (which serves as a game controller), a depth camera (e.g. Kinect), a personal computer, and a virtual world software application with mini- games designed to sustain engagement in remotely monitored home-based therapy. Software includes mini-games such as Feeding Time and Flight School (shown in Figure 1) that are designed to support mass practice of UE reaching movement involving the shoulder, elbow, and hand. For example, in Feeding Time the player uses the smart toy to capture dragon food and bring it to the hungry baby dragon. Each movement to capture the food and then bring it to the dragon requires a point-to-point UE reaching movement. Target positioning for these reaching movements (the food and the dragon) is designed to elicit a specific degree of movement, determined by participating pediatric rehabilitation doctors and OTs, and categorized by difficulty and movement type to permit tailoring of the game for the individual patient. Note that the avatar's arm in the game moves according to the sensor-derived arm joint angles, not hand position. This has the important effect of making level of difficulty for a given movement invariant to the child's arm length (a 4-year-old and 14-year-old will experience that same challenge in reaching the food and feeding the dragon). As

another example, the Flight School mini-game is designed to challenge the child's range of motion in forearm supination, an important movement in therapy for pediatric hemiplegia. The game translates the player's pronation/supination movements into left-right steering of the baby dragon's flight. The player uses these movements to steer the dragon through a series of targets to gain speed and collect rewards.

Figure 1. MOVE-IT system in use during Phase I pilot testing

The NIH-sponsored MOVE-IT Phase II program culminates in a rater-blinded randomized, controlled trial to investigate efficacy of a MOVE-IT based intervention in home use by children with hemiplegia, as measured by change in gold-standard measures of UE

function for a cohort using MOVE-IT compared to a usual care treatment (UCT) group. The University of Virginia (UVA) will serve as coordinating center and single IRB (sIRB) for a two-site MOVE-IT RCT that includes UVA and Duke University. Overall direction of the RCT will be provided by [name], M.D., Head, Division of Developmental Pediatrics, UVA School of Medicine and former President of the American Academy for Cerebral Palsy and Developmental Medicine. Participation of the Duke University site will be under the direction of pediatric rehabilitation specialist [name], M.D.

#### 2.2 Scientific Rationale

Hemiplegia is a partial paralysis or weakness of one side of the body that impairs the use of the UE on the affected side and disrupts motor functions essential to self-care, play, exploratory learning, and daily activities. Causes of pediatric hemiplegia encompass any injury or illness associated with the brain, including cerebral palsy (CP), cerebral vascular accident (stroke), traumatic brain injury, brain tumor, or other illness [1]. CP impacts more than 1 in 300 children, with disproportionate prevalence in minority and economically disadvantaged populations [2]. Prevalence of CP has been reported to be 50-100% higher among black or African American children than other demographics [3]. Overall, 60% of children with CP experience some level of impairment in UE function [4], which can include reduced range of motion (e.g. in the shoulder in the frontal plane [5] and in forearm pronation/supination [6]) and the presence of significant compensatory movement (especially of the trunk). Stroke is a form of acquired brain injury caused by an occlusion or rupture of blood vessels [1]. Although more commonly associated with adults, stroke impacts individuals of all ages, including children [7].

Usual care for pediatric hemiplegia includes occupational therapy (OT) as well as adjunct therapies, such as spasticity-reducing medications. These approaches to upper-limb therapy can be considered effective to the extent they improve independence and a child's ability to meet individual goals [8].

Systematic reviews strongly support that constraint-induced movement therapy (CIMT) is one of the most effective treatments for pediatric hemiplegia [9], [10], [11], [12], [13], [14]. In CIMT, the less affected UE is constrained (i.e. typically employing a cast or mitt) while the impaired limb is engaged in intensive, repetitive, activity-based training [15], [16]. When considering alternate approaches, higher duration of training is consistently associated with better outcomes [17], [18], [8]. Meta-analysis examining 42 randomized and controlled trials involving UE interventions (n = 1454 subjects) found moderate to strong evidence supporting the superiority of intensive, task-directed training over usual care [19]. These regimes are associated with superior outcomes in spontaneous use, quality of movement, and task performance [20], [21].

Neuroplasticity provides one possible explanation for why increased dosage/intensity produces superior outcomes over usual care. Brain plasticity can be defined as the formation of new circuits and changes to internal structures that remap existing synapses to perform functions previously accomplished by injured cortical tissue [22], [23]. Although the relationship between therapy for pediatric hemiplegia and brain neuroplasticity is only beginning to be understood, emerging evidence appears to mirror findings in stroke research that frequent, longer-duration interventions improve cortical activation and neuroplasticity, and thus lead to better outcomes [24], [25]. Functional MRI results appear to show that intensive training can produce neuroplastic changes on the synaptic level in children with CP, evidenced by increased task-related brain activation in the lesioned region of the primary motor cortex [26], [27], [28].

New intensive therapy regimes strain the capacity and resources of delivery systems and challenge the creativity of individual therapists to maintain patient engagement and motivation. Total dosages for CIMT in clinical trials have involved up to 126 hours of therapist-supervised training [20]. A study comparing efficacy of 30 vs. 60 hours of CIMT for children with unilateral CP found 60 hours to be sufficient, but 30 insufficient, to achieve desired outcomes [29]. When reducing CIMT dosage to numbers more typical for usual care, outcomes fall short compared to more intensive training [29]. It thus appears that 50-60 hours are needed in clinical practice [30], but delivering such dosages strains the capacity of existing health systems and can exceed the reimbursement limits of insurers. Using delivery mechanisms typical of usual care, a 1-to-1 child-to-therapist ratio may be required to achieve adequate dosage [29]. Individual therapists also face the formidable challenge of keeping patients motivated in more frequent and longer practice sessions.

#### 2.3 Potential Risks and Benefits

#### 2.3.1 Potential Risks

Potential risks are described below, along with mitigation measures that will be implemented by the study team.

- (1) Soreness, pain, or increased tone post-use due to increased range and level of activity involving the upper extremity.
- a. Game-integrated movements will be consistent with accepted clinical practice for occupational therapy and exercises used in previous RCTs involving intensive therapy (e.g. the CHAMP R01 program RCT, NCT01895660.);
- b. Subjects will be reminded to take frequent breaks.
- c. Study staff will ensure families understand that they can withdraw from the study at any time without reason or consequence.
- d. At least once every two weeks, study staff will contact the participant by phone or HIPAA compliant video conferencing to collect self-reported adherence data and confirm that no change in medical status has occurred that would impact

- continued participation. The staff member will inquire regarding soreness, pain, or increased tone and consult with the PI if any concerns are reported.
- (2) Elevated stress or embarrassment due to frustration with the interface or inability to perform a task.
- a. Initial visits with licensed pediatric therapists assesses appropriateness of MOVE-IT use for the individual patient and the home environment;
- b. Physical and cognitive demands are progressive and appropriate for the participant population and consistent with existing clinical practice; and
- c. At least once every two weeks, study staff will contact the participant by phone or HIPAA compliant video conferencing. If elevated stress, embarrassment, or frustration are reported, a study pediatric therapists will adjust the activity settings and follow up with the parent or guardian to ensure the issue is resolved. If the issue cannot be resolved to the satisfaction of the therapist and parent, the PI will be consulted regarding appropriateness of continued participation.
- (3) Risk of accidental release of identifying and/or confidential information.
- a. Potential risks of accidental release of identifying and/or confidential information will be mitigated by use of a coded identifier key for all participant data and implementation of detailed measures described in the Data Security Plan.

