#### MOVE-IT HEP Independent Practice at Home

- Participants will be asked to employ the GRASP system for UE practice at home for a total of 1 hour/day, 5 days/week over the 10-week intervention period.
- Patients will continue to perform any previously prescribed therapy.

- Once per week during this period, non-blinded study staff will employ an authorized web application on a UVA computing system to remotely monitor de-identified participant data (see Data Security Plan for details) that includes exercise adherence (duration performed), movement repetitions accomplished (exercise reps), and exercise intensity (speed).
- At least once every two weeks, non-blinded study staff will contact the participant by phone or HIPAA compliant video conferencing to collect self-reported adherence data and confirm that no change in medical status has occurred that would impact continued participation.

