#### **GROUP 2: UCT GROUP:**

- Participants in the control group will continue to receive any previously prescribed therapy services. These patients will not receive any treatment services through the study as UCT group participants.
- At least once every two weeks during the interventional period, non-blinded study staff will contact the participant by phone or HIPAA compliant video conferencing to collect self-reported adherence data and confirm that no change in medical status has occurred that would impact continued participation.

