#### 7.4 Analysis Plan

Primary variable analysis involves analysis of completion times for each of the seven tasks in the JTHFT which will be summed to produce a total score. The pre-intervention scores will be subtracted from the post-intervention scores to produce a set of delta values. These delta values scores ( $\Delta$ ) will be analyzed via Analysis of Covariance (ANCOVA). One null hypothesis will test if the mean pre-to-post-intervention change in the total JTHFT score is equal to zero, while the second null hypothesis will test if the mean pre-to post-intervention change in the JTHFT score is the same for patients who participate in a 10-week MOVE-IT HEP and patients who under UCT over the same duration. For both null hypotheses, a p $\leq$ 0.05 decision rule will be utilized as the rejection criterion. Analysis of data from the 3-month follow-up assessment will be performed in a similar manner.

Secondary variable analysis includes analysis of the pre-to-post intervention changes in the composite WMFT scores which will be analyzed in the same way as the pre-to-post intervention change in the composite JTHFT scores. The same method of analysis will be used to analyze the pre-to-post intervention changes in the QUEST scores.

The Likert scale responses to the SUS questionnaire will be summarized per question, and per question category, by frequencies and percentages. As an overall measure of system usability, a composite SUS score in the range from 0 to 100 will be derived from individual responses. By convention, a SUS score greater than or equal to 68 is indicative of an efficient, effective, and satisfying system. For the TAM questionnaire, percentages of favorable responses to the questions of each topic will be estimated via a binomial generalized estimating equation model, and a 90% confidence interval constructed. A Wald test will be used to test the null hypothesis that the odds of a favorable response are independent of the question topic.

Therapy session adherence and activity will be assessed by way of a binomial generalized estimating equation model, in which therapy adherence and activity measures (collected via parental logs) will be compared between the patients who participate in a 10-week MOVE-IT HEP and patients under UCT over the same duration.

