#### 8 SUBJECT CONFIDENTIALITY

Subject confidentiality is held strictly in trust by the participating investigators, their staff, the sponsor, and their agents. The study protocol, documentation, data, and all other information generated will be held in strict confidence. No information concerning the study, or the data will be released to any unauthorized third party without prior written approval of the sponsor. The clinical study site will permit access to appropriate documents and records that may require inspection by the sponsor or its authorized representatives including de-identified study data.

Only IRB-registered protocol staff will have access to the actual identities of the participants, which will remain anonymous to all non-IRB authorized persons.

The sources of human research data will include the following.

- 1. Demographic information, including age, sex, race, and ethnicity.
- 2. Results of screening instruments.
- 3. Rater-blinded assessment instruments including: JTHFT, QUEST, and WMFT.
- 4. Parental report instrument Pediatric Motor Activity Log.
- 5. MOVE-IT game-derived measures including achieved therapy duration, and functional movement repetitions.
- 6. Weekly activity logs
- 7. SUS and TAM usability questionnaires
- 8. Transcribed usability data including think-aloud expressions during system use; captured in digital video, screen captures, and therapist notes.

Potential risks of accidental release of identifying and/or confidential information will be mitigated by use of a de-identified coded key for all subject data. The cipher that relates participants to the key will exist in hard (paper) copy only and be stored in a locked cabinet in a controlled-access room at the study sites. All data sheets will be properly controlled and shredded prior to disposal.

De-identified data covering primary and secondary measures will be analyzed by the study biostatistician. The de-identified data and the results of biostatistical analysis will be provided to the sponsor via encrypted means. Results will be reported by the sponsor to the NIH via annual and final progress reports, and incorporated into one or more manuscripts to be submitted for publication in

medical journals and/or conference proceedings accessible via PubMed Central. ClinicalTrials.gov and results information will be submitted according to ClinicalTrials.gov	RCT will	be register	ed with

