# 10 DATA AND SAFETY MONITORING PLAN-IRB-HSR TO SERVE AS SIRB OF RECORD

This study has been deemed minimal risk. Because this study poses minimal risk to the subject, adverse events will only be collected or recorded if a causal relationship to the study intervention is suspected. If any adverse event is considered serious and unexpected, the event must be reported to the IRB-HSR within 7 days from the time the study team receives knowledge of the event.

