#### 10.1 Definitions

#### 10.1.1 How will you define adverse events (AE)?

Do not change this answer

An adverse event will be considered any undesirable sign, symptom or medical condition considered **related to the intervention**. Medical condition/diseases present before starting the intervention will be considered adverse events only if they worsen after starting the study and that worsening is considered to be related to the study intervention. An adverse event is also any undesirable and unintended effect of research occurring in human subjects as a result of the collection of identifiable private information under the research.

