#### 10.2 What risks are expected due to the intervention in this protocol?

Expected Risks related to study participation	Pick One
There is a small risk that breaches of privacy and/or	Occurs rarely
confidentiality might occur. The risk of violation of subject	
privacy and confidentiality is minimal due to the requirements	
of the privacy plan in this protocol.	
There is a minor risk that soreness, pain, or increased tone	Occurs rarely
may occur post-use due to increased range and level of	
activity involving the upper extremity. The risk is minor as	
game-integrated movements are consistent with accepted	

clinical practice and exercises used in previous RCTs involving	
similar therapy (e.g. the CHAMP R01 RCT, [12]).	
There is a minor risk of elevated stress or embarrassment due	Occurs rarely
to frustration with the interface or inability to perform a task.	
The risk is minor as cognitive demands are progressive and	
appropriate for the participant population and consistent with	
existing clinical practice. Study pediatric therapists will tailor	
the activities to the capabilities of the patient.	

10.3 When will recording and	reporting of unanticipated	problems/adverse events begin?
------------------------------	----------------------------	--------------------------------

\_\_x\_\_\_After subject begins study intervention

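### The one named physical harm would be recorded only when suspected to be related to MOVE-IT, so in effect in the HEP arm alone, with no control comparison and no planned summary

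*Combined protocol and SAP*

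**What the plan says.** Section 2.3.1 lists soreness, pain or raised tone after use as the first potential risk. Among the mitigations is a contact at least every two weeks, at which "The staff member will inquire regarding soreness, pain, or increased tone and consult with the PI if any concerns are reported". Section 10.2 lists the same harm and rates it as occurring rarely.

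Section 6.1 schedules the contact in both arms. For HEP: "At least once every two weeks, non-blinded study staff will contact the participant by phone or HIPAA compliant video conferencing". For UCT: "At least once every two weeks during the interventional period, non-blinded study staff will contact the participant by phone or HIPAA compliant video conferencing". In both places the stated content is adherence and any change in medical status; the symptom question is not repeated in either.

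Section 10 limits what is kept: "adverse events will only be collected or recorded if a causal relationship to the study intervention is suspected". Section 10.1.1 builds relatedness into the definition: "An adverse event will be considered any undesirable sign, symptom or medical condition considered" related to the intervention. Section 10.3 sets the start of recording: "After subject begins study intervention". Section 10.5 provides for aggregate review by the PI and the IRB at least annually and states no split by arm.

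Section 7.4 covers JTHFT, WMFT, QUEST, SUS, TAM and adherence. Besides the function tests, its only comparison between arms is that "therapy adherence and activity measures (collected via parental logs) will be compared between the patients who participate in a 10-week MOVE-IT HEP" and UCT. It contains no harm summary.

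**The concern.** MOVE-IT asks a child for an hour of arm practice a day, five days a week, for ten weeks, on top of any therapy already prescribed. Both arms continue that prescribed therapy, so soreness or raised tone can occur without MOVE-IT. A record restricted to events that someone suspects the device caused cannot separate the two, because it depends on a case-by-case judgement and has no background level beside it.

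A randomised control group is the direct way to supply that background, and the trial already has one that is telephoned on the same schedule. At stake is whether the trial can say anything comparative about the one physical harm it expects, including whether rare is a fair description. Efficacy and the protection of individual children are not at stake.

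**Working it through.** **Step 1. Follow a sore child through the plan.**

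| | HEP child | UCT child |
|---|---|---|
| Contact at least every two weeks (6.1) | Yes | Yes |
| Symptom question asked (2.3.1) | Yes | Not settled: no arm is named, but the risk is framed as arising after use, and the UCT call content in 6.1 omits it |
| Stated action if a concern is reported (2.3.1) | Consult the PI | Consult the PI, if asked |
| Recorded as an adverse event (10, 10.1.1, 10.3) | Only if a link to the intervention is suspected | By inference no: there is no study intervention to be linked to, or to start the recording period |
| Summarised (7.4) | Not planned | Not planned |

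That only HEP children can contribute is an inference. It combines the relatedness rule, the start of recording, and the statement in 6.1 that UCT children get no treatment through the study. They are offered MOVE-IT only after the control protocol is complete.

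**Step 2. Inputs.** Section 7.2 plans 24 children per group. This agrees with its own arithmetic: 40 completers / (1 - 0.15) = 47.06, rounded up to 48 for equal groups. Calls: 10 weeks / 2 = at least 5 per child, so 5 x 24 = 120 per arm and 240 in all if everyone stays in. The documents give no numerical symptom rate, so all event counts below are assumed.

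**Step 3. What a comparison by arm would show.** The interval is Newcombe's, built from Wilson limits (l, u) for each arm, with d = p1 - p2:

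- lower = d - sqrt[(p1 - l1)^2 + (u2 - p2)^2]
- upper = d + sqrt[(u1 - p1)^2 + (p2 - l2)^2]

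Worked case, 6/24 vs 2/24, in percentage points. The Wilson limits are 12.00 to 44.90 and 2.32 to 25.85, and d = 25.00 - 8.33 = 16.67.

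- lower = 16.67 - sqrt(13.00^2 + 17.52^2) = 16.67 - 21.82 = -5.15
- upper = 16.67 + sqrt(19.90^2 + 6.02^2) = 16.67 + 20.79 = 37.46

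| Assumed children with a report, HEP vs UCT (24 per arm) | Difference, points | 95% CI |
|---|---|---|
| 1 vs 0 | 4 | -10 to 20 |
| 2 vs 1 | 4 | -13 to 22 |
| 2 vs 0 | 8 | -7 to 26 |
| 6 vs 2 | 17 | -5 to 37 |
| 6 vs 0 | 25 | 6 to 45 |

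The first three rows are closest to the protocol's own description of the harm as rare, and all include zero. Only the last row excludes zero, and it needs no report at all from any control child over ten weeks.

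**The case against.** The case for leaving the plan alone is substantial. The study is classed as minimal risk, has no safety objective, and its related-only definition is fixed IRB template text. The plan is coherent in its own terms: ask, take concerns to the PI, record if a link is suspected. At the rate the protocol expects, a comparison of 24 with 24 will be imprecise. Families are not blinded, so HEP parents who have been warned of soreness may report more of it, and the comparison would exchange a causality judgement for a reporting bias. All of this stands. It limits the value of the change but does not supply the missing comparator.

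Three stronger readings should be resisted.

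- **The section 8 list shows the answers will not be kept.** It does not. The list opens "The sources of human research data will include the following", which need not be exhaustive, and it also leaves out adverse-event records, which section 10 plainly requires. The point does not rely on it.
- **Control-arm answers are being collected and discarded.** The documents do not establish that UCT families are asked. If they are not, the proposal adds new questions to the control calls.
- **Only events firmly judged related are kept.** Section 10 says suspected, which is a lower bar, and arm soreness during daily arm exercise would often meet it. The protocol also promises no formal count, only recording and aggregate review.

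**Conclusion.** The point holds as a cheap, optional improvement. As written, the trial's planned record of its one named physical harm consists of HEP events suspected to be related, with no concurrent comparator and no planned summary. This follows from stated rules on what is recorded and from when; it is not just missing detail.

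The benefit is modest. At low assumed counts the difference is 4 to 8 points, with limits reaching from -13 to 26; at higher assumed counts it is 17 to 25 points, with limits from -5 to 45. These rest on 24 children per arm and on illustrative counts. A reader might infer that children are left unprotected or that the efficacy result is affected. Neither is supported: concerns go to the PI in any case, and the JTHFT comparison is untouched.

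**What to change.** 1. **Section 6.1, both groups.** At the baseline visit and at each fortnightly call, ask in the same words whether the child has had (a) soreness, (b) pain, (c) increased tone in the affected arm (on the calls, since the last contact). Record yes or no for each, whatever the suspected cause. Baseline answers matter because children with hemiplegia may already have raised tone. The baseline visit precedes assignment and the calls are made by non-blinded staff, so the raters' blinding is not put at risk.
2. **Section 7.4.** For each symptom, report by assigned group the number and percentage of children with at least one report and the proportion of completed calls with a report. Give the HEP-minus-UCT difference in the proportion of children with a Newcombe 95% CI. State that this is descriptive, with no hypothesis test.
3. **Section 10.** Leave unchanged.

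The cost is three short items at one visit and on calls already scheduled, one table, and a few lines of protocol text; no extra visits or staff are needed. If UCT families are not currently asked, the items are new for them. The report should say that the intervals are wide, that unblinded HEP families may over-report, and that a parent's yes or no on increased tone is a crude measure.
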